Appendix B. Inclusion/Exclusion Form

1029259 Real-World Impact of RA

	-		
--	---	--	--

Site number Participant ID

Patient Inclusion/Exclusion Form

Today's date:

--	--

 /

--	--

 /

--	--	--	--

Month Day Year

Please check if the patient meets all of the following inclusion criteria.

• Subject has a diagnosis of RA as defined by the 1987 revised ACR classification criteria and/or the ACR/EULAR 2010 classification criteria (any duration since diagnosis)	 Yes  No
• Male or female subject ≥ 18 years of age (local definition according to adalimumab label) who is in compliance with eligibility for adalimumab based on the local label	 Yes  No
• With moderate to severe RA defined as DAS28 (ESR) or DAS28 (CRP) > 3.2	 Yes  No
• Biologically treatment naïve and initiated adalimumab at baseline visit	 Yes  No
• Availability of clinical data of the previous 12 weeks prior to baseline	 Yes  No
• Ability to self-complete patient questionnaires	 Yes  No
• Subject must be able and willing to provide written informed consent and comply with the requirements of the study protocol	 Yes  No

The patient can only be enrolled with 'Yes' checked for all inclusion criteria above.

Please check if the patient meets any of the following exclusion criteria.

• The patient is pregnant or breast feeding at enrolment or wishes to become pregnant in the next 24 weeks	 Yes  No
• Participation in any RA-related clinical trial at the time of enrolment, at baseline or at any point during the past 24 weeks prior to baseline	 Yes  No
• The patient, who in your view, may not be able to accurately report their quality of life or prior resource utilization	 Yes  No
• The patient, who in your view, may not be able to adhere to adalimumab therapy over 24 weeks	 Yes  No

The patient can only be enrolled with 'No' checked for all exclusion criteria above.

Appendix C. Clinical Case Report Form (CRF)

Baseline:

1023259 Real-World Impact of RA
[Site number] - [Participant ID]

Clinician Case Report Form (Baseline)

All of the following information must be completed by the clinician or his/her representative.

Clinician name: _____

Clinician signature: _____

Patient ID	[Site #]	-	[Participant #]		
Today's date	[Day]	/	[Month]	/	[Year]

Please provide the information below.	
1. When was the patient diagnosed with Rheumatoid Arthritis?	[Year]
2. What is the patient's current disease status?	 Moderate  Severe

1023259 Real-World Impact of RA
 -
Site number Participant ID

Please provide the information below.		
3. Please perform a swollen and tender joint examination on your patient using the figure below and record the total number of tender/swollen joints in the appropriate boxes on the right.	 Tender Joint Count	 Swollen Joint Count
If diagnosis is RA:		
4. Please record the most recent Erythrocyte Sedimentation Rate (ESR) (in mm/hour) or C-reactive protein (CRP) (in mg/L) of this patient.	 ESR (mm/hour) Test Date (DD/MM/YYYY): ____/____/_____  CRP (mg/L) Test Date (DD/MM/YYYY): ____/____/_____ 5. Please record the latest DAS28 score*, if calculated	

* For calculation instruction, please refer to study protocol, page 21, clinical case report form (CRF).

1023259 Real-World Impact of RA
[REDACTED]
[REDACTED]
Site number - Participant ID

6. Please check all the comorbidities this patient has currently.

- ₀ No comorbidity
- ₁ Myocardial infarction
- ₂ Congestive heart failure
- ₃ Peripheral vascular disease
- ₄ Cerebrovascular disease
- ₅ Dementia
- ₆ Chronic pulmonary disease
- ₇ Connective tissue disease
- ₈ Ulcer disease
- ₉ Mild liver disease
- ₁₀ Diabetes
- ₁₁ Hemiplegia
- ₁₂ Moderate or severe renal disease
- ₁₃ Diabetes with end-organ damage
- ₁₄ Any tumor
- ₁₅ Leukemia
- ₁₆ Lymphoma
- ₁₇ Moderate or severe liver disease
- ₁₈ Metastatic solid tumor
- ₁₉ AIDS

1023259 Real-World Impact of RA
[REDACTED]
Site number - Participant ID

7. Please check all the prior medications this patient has received for her/his Rheumatoid Arthritis in the last 6 months.
(No response option for biologics is given as the current study recruits only patients with no history of any biologics prior to the study).

Drug Name	Average number of pills per day	Dose strength	Times per month
Disease Modifying Antirheumatic Drug (DMARD)			
 ₁ Auranofin (Ridaura, Myochrysine)	_____	_____ mg	_____
 ₂ Azathioprine (Imuran)	_____	_____ mg	_____
 ₃ Cyclosporine (Sandimmune and Neoral)	_____	_____ mg	_____
 ₄ Hydroxychloroquine (Plaquenil)	_____	_____ mg	_____
 ₅ Leflunomide (Arava)	_____	_____ mg	_____
 ₆ Methotrexate (Rheumatrex, Folex)	_____	_____ mg	_____
 ₇ Minocycline (Minocin, Dynacin and Vectrin)	_____	_____ mg	_____
 ₈ Sulfasalazine (Azulfidine)	_____	_____ mg	_____
 ₉ Others	_____	_____ mg	_____
Anti-inflammatory Drug (NSAID)			
 ₁₀ Ibuprofen (Advil, Motrin, Nuprin)	_____	_____ mg	_____
 ₁₁ Naproxen (Naprosyn, Anaprox, Aleve)	_____	_____ mg	_____
 ₁₂ Celecoxib (Celebrex)	_____	_____ mg	_____
 ₁₃ Aspirin (ASA)	_____	_____ mg	_____
 ₁₄ Diclofenac (Voltaren)	_____	_____ mg	_____
 ₁₅ Indomethacin (Indocid)	_____	_____ mg	_____
 ₁₆ Others	_____	_____ mg	_____
Others			
 ₁₇ Steroids	_____	_____ mg	_____
 ₁₈ Stomach or gastric medications	_____	_____ mg	_____

1023259 Real-World Impact of RA
[Site number] - [Participant ID]

8. Please check all the prior surgeries this patient has received for her/his Rheumatoid Arthritis in the last 6 months.			
 No surgery performed			
 Yes → Type of Surgery (Please input the number of the list below)			
 1	_____	_____ days	_____/_____/____
 2	_____	_____ days	_____/_____/____
 3	_____	_____ days	_____/_____/____
 4	_____	_____ days	_____/_____/____
 5	_____	_____ days	_____/_____/____
List of common surgeries for rheumatoid arthritis:			
1. Arthroscopy 2. Carpal tunnel release 3. Cervical spinal fusion 4. Total knee replacement 5. Total hip replacement 6. Knee arthrodesis (fusion) 7. Hip arthrodesis (fusion) 8. Synovectomy 9. Other: _____			

* For day surgeries, please input 0 days.

1023259 Real-World Impact of RA
[REDACTED]
[REDACTED]
Site number - Participant ID

9. Please check any Hylan G-F 20 (Synvisc) injection this patient has received for her/his Rheumatoid Arthritis in the last 6 months.

 No injection performed	Injection Place	Dosage	Number of Shots
 Yes →	 Hip	_____ ml	_____
	 Knee	_____ ml	_____

10. Please provide the dosing information for the first injection of Adalimumab (Humira) this patient has received for her/his Rheumatoid Arthritis.

First time administration (DD/MM/YYYY):	Dosage
____/____/____	_____ mg

1023259 Real-World Impact of RA
[REDACTED]
Site number - Participant ID

[figure not shown]
11. Please record the current medications this patient has received for her/his Rheumatoid Arthritis.

Drug Name	Average number of pills per day	Dose strength	Times per month
Disease Modifying Antirheumatic Drug (DMARD)			
 ₁ Auranofin (Ridaura, Myochrysine)	_____	_____ mg	_____
 ₂ Azathioprine (Imuran)	_____	_____ mg	_____
 ₃ Cyclosporine (Sandimmune and Neoral)	_____	_____ mg	_____
 ₄ Hydroxychloroquine (Plaquenil)	_____	_____ mg	_____
 ₅ Leflunomide (Arava)	_____	_____ mg	_____
 ₆ Methotrexate (Rheumatrex, Folex)	_____	_____ mg	_____
 ₇ Minocycline (Minocin, Dynacin and Vectrin)	_____	_____ mg	_____
 ₈ Sulfasalazine (Azulfidine)	_____	_____ mg	_____
 ₉ Others	_____	_____ mg	_____
Anti-inflammatory Drug (NSAID)			
 ₁₀ Ibuprofen (Advil, Motrin, Nuprin)	_____	_____ mg	_____
 ₁₁ Naproxen (Naprosyn, Anaprox, Aleve)	_____	_____ mg	_____
 ₁₂ Celecoxib (Celebrex)	_____	_____ mg	_____
 ₁₃ Aspirin (ASA)	_____	_____ mg	_____
 ₁₄ Diclofenac (Voltaren)	_____	_____ mg	_____
 ₁₅ Indomethacin (Indocid)	_____	_____ mg	_____
 ₁₆ Others	_____	_____ mg	_____
Others			
 ₁₇ Steroids	_____	_____ mg	_____
 ₁₈ Stomach or gastric medications	_____	_____ mg	_____

Thank you for completing the Clinician Case Report Form.
Please return this form to the IMS representative.

Follow-up:

1023259	Real-World Impact of RA
Site number	Participant ID

Clinician Case Report Form (Follow-up)

All of the following information must be completed by the clinician or his/her representative.

Clinician name: _____

Clinician signature: _____

[figure not shown]
[figure not shown]
Site & participant ID

Today's date: / /

Please provide the information below.		
1. What is the patient's current disease status?	 Moderate	 Severe

1023259 Real-World Impact of RA

100

Please provide the information below.
 
2. Please perform a swollen and tender joint examination on your patient using the figure below and record the total number of tender/swollen joints in the appropriate boxes on the right.
		 	Tender Joint Count	 	Swollen Joint Count

If diagnosis is RA:
 
 
  
 
  
 
					

3. Please record the most recent Erythrocyte Sedimentation Rate (ESR) (in mm/hour) or C-reactive protein (CRP) (in mg/L) of this patient.
			
   ESR (mm/hour)
 
   CRP (mg/L)
		

4. Please record the latest DAS28 score*, if calculated
					

* For calculation instruction, please refer to study protocol, page 21, clinical case report form (CRF).

1023259 Real-World Impact of RA
[Site number] - [Participant ID]

[figure not shown]
5. Please check all the surgeries this patient has received for her/his Rheumatoid Arthritis since the last completed survey.			
 No surgery performed			
 Yes →	Type of Surgery (Please input the number of the list below)	Length of Stay*	Date of surgery (DD/MM/YYYY)
	 1 _____	_____ days	_____/_____/_____
	 2 _____	_____ days	_____/_____/_____
	 3 _____	_____ days	_____/_____/_____
	 4 _____	_____ days	_____/_____/_____
	 5 _____	_____ days	_____/_____/_____
List of common surgeries for rheumatoid arthritis:			
1. Arthroscopy 2. Carpal tunnel release 3. Cervical spinal fusion 4. Total knee replacement 5. Total hip replacement 6. Knee arthrodesis (fusion) 7. Hip arthrodesis (fusion) 8. Synovectomy 9. Other: _____			

* For day surgeries, please input 0 days.

6. Please check any Hylan G-F 20 (Synvisc) injections this patient has received for her/his Rheumatoid Arthritis since the last completed survey.			
 No injection performed			
 Yes →	Injection Place	Dosage	Number of shots
	 1 Hip	_____ ml	_____
	 2 Knee	_____ ml	_____

1023259 Real-World Impact of RA

			-			
Site number	Participant ID					

7. Please check any adalimumab (Humira) injection this patient has received for her/his Rheumatoid Arthritis since the last completed survey.						
 No, no injection performed		Dosage	Number of Times			
 Yes →			_____ mg	_____		
Administration stop date (if stopped)		____/____/____ (DD/MM/YYYY)				

1023259 Real World Impact of RA
[Site number] - [Participant ID]

8. Please record all of the medications this patient has received for her/his Rheumatoid Arthritis since the last completed survey			
Drug Name	Average number of pills per day	Dose strength	Times per month
Disease Modifying Antirheumatic Drug (DMARD)			
 ₁ Auranofin (Ridaura, Myochrysine)	_____	_____ mg	_____
 ₂ Azathioprine (Imuran)	_____	_____ mg	_____
 ₃ Cyclosporine (Sandimmune and Neoral)	_____	_____ mg	_____
 ₄ Hydroxychloroquine (Plaquenil)	_____	_____ mg	_____
 ₅ Leflunomide (Arava)	_____	_____ mg	_____
 ₆ Methotrexate (Rheumatrex, Folex)	_____	_____ mg	_____
 ₇ Minocycline (Minocin, Dynacin and Vectrin)	_____	_____ mg	_____
 ₈ Sulfasalazine (Azulfidine)	_____	_____ mg	_____
 ₉ Others	_____	_____ mg	_____
Anti-inflammatory Drug (NSAID)			
 ₁₀ Ibuprofen (Advil, Motrin, Nuprin)	_____	_____ mg	_____
 ₁₁ Naproxen (Naprosyn, Anaprox, Aleve)	_____	_____ mg	_____
 ₁₂ Celecoxib (Celebrex)	_____	_____ mg	_____
 ₁₃ Aspirin (ASA)	_____	_____ mg	_____
 ₁₄ Diclofenac (Voltaren)	_____	_____ mg	_____
 ₁₅ Indomethacin (Indocid)	_____	_____ mg	_____
 ₁₆ Others	_____	_____ mg	_____
Others			
 ₁₇ Steroids	_____	_____ mg	_____
 ₁₈ Stomach or gastric medications	_____	_____ mg	_____

Thank you for completing the Clinician Case Report Form.
Please return this form to the IMS representative.

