9.2.4.7 Study Documents

Clinical case report form (CRF)

The clinical CRF will document the patient's current status (moderate, severe RA), Disease Activity Score in 28 joints (DAS28), prior and current treatments and other relevant clinical and demographic data to be used in segmenting the population during analysis.

To calculate the DAS28 the physician or specialist nurse will:

1. Count the number of swollen joints (out of the 28)
2. Count the number of tender joints (out of the 28)
3. Record the blood test data of erythrocyte sedimentation rate (ESR) or C reactive protein (CRP) using the latest measurement in the medical records
4. Record the 'global assessment of health' of patients, which will be indicated by marking a 10 cm line between very good and very bad

The physician or specialist nurse will then mark each component score on the CRF and the DAS28 score if calculated (an online scoring calculator for the DAS28 can be found at [REDACTED])

The DAS28 will be scored using the following formula:

$$\text{DAS28 ESR} = 0.56 * \text{sqrt}(\text{tender28}) + 0.28 * \text{sqrt}(\text{swollen28}) + 0.70 * \ln(\text{ESR}) + 0.014 * (\text{Global assessment of Health in cm})$$

$$\text{DAS28 CRP} = 0.56 * \text{sqrt}(\text{tender28}) + 0.28 * \text{sqrt}(\text{swollen28}) + 0.36 * \ln(\text{CRP}) + 0.014 * (\text{Global assessment of Health in cm}) + 0.96$$

DAS28 scores will be interpreted using the following categorization:

- Remission: $DAS28 \leq 2.6$
- Low Disease activity: $2.6 < DAS28 \leq 3.2$
- Moderate Disease Activity: $3.2 < DAS28 \leq 5.1$
- High Disease Activity: $DAS28 > 5.1$

The full CRF is presented in Appendix C.

PRO questionnaires

The following PRO questionnaires will be included in the patient questionnaire packet.

Health Assessment Questionnaire Disability Index (HAQ DI)

The HAQ DI is a patient-reported questionnaire to assess functioning impacted by RA. It includes the categories of dressing and grooming, arising, eating, walking, hygiene, reach, grip and common daily activities. It asks patients about the amount of difficulty they experience in these activities as well as the use of aids and/or devices. The HAQ also has a numeric rating scale (NRS) (13) to assess pain on a scale from 0 to 10. Self-administered by the patient, the completion time is approximately 3-4 minutes. The full version of HAQ DI is presented in Appendix D.

Short Form (36) Health Survey (SF-36)

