 - Age at baseline
 - Age groups
 - Gender at birth
 - Marital status (married, unmarried)
 - Medical plan type
 - ✓ The type of healthcare plan each patient is enrolled in at baseline will be determined, including National/Public insurance, Private insurance, Employer benefits, and Other
- **Clinical characteristics**
 - Initial Diagnosis of Rheumatoid Arthritis (RA)
 - ✓ Year of initial diagnose
 - Initiation of Adalimumab
 - ✓ First time administration (DD/MM/YYYY)
 - ✓ Dosage of first injection (in mg)
 - Disease status of RA
 - ✓ Moderate (defined as Disease Activity Score in 28 Joints (DAS28) between 3.2 and 5.1)
 - ✓ Severe (DAS28>5.1)
 - Erythrocyte sedimentation rate (ESR) (in mm/hour)
 - C reactive protein (CRP) (in mg/L)
 - Disease Activity Score in 28 joints (DAS28)

To calculate the DAS28, the physician or specialist nurse will:

1. Count the number of swollen joints (out of the 28)
2. Count the number of tender joints (out of the 28)
3. Take blood to measure the erythrocyte sedimentation rate (ESR) or C reactive protein (CRP); the latest measurement in the medical records may also be used if a blood draw is not standard for that visit

4. Ask the patient to make a 'global assessment of health' which will be indicated by marking a 10 cm line between very good and very bad

The physician or specialist nurse will then mark each component score on the CRF and the DAS28 score if calculated (an online scoring calculator for the DAS28 can be found at <http://www.das-score.nl/das28/DAScalculators/dascalculators.html>).

The DAS28 will be scored using the following formula:

$$\text{DAS28} = 0.56 * \text{sqrt}(\text{tender28}) + 0.28 * \text{sqrt}(\text{swollen28}) + 0.70 * \ln(\text{ESR or CRP}) + 0.014 * (\text{Global assessment of Health})$$

DAS28 scores will be interpreted using the following categorization:

- ✓ Remission: DAS28 \leq 2.6
- ✓ Low Disease Activity: $2.6 < \text{DAS28} \leq 3.2$
- ✓ Moderate Disease Activity: $3.2 < \text{DAS28} \leq 5.1$
- ✓ High Disease Activity: DAS28 > 5.1

– comorbidities

- ✓ Myocardial infarction
- ✓ Congestive heart failure
- ✓ Peripheral vascular disease
- ✓ Cerebrovascular disease
- ✓ Dementia
- ✓ Chronic pulmonary disease
- ✓ Connective tissue disease
- ✓ Ulcer disease
- ✓ Mild liver disease
- ✓ Diabetes
- ✓ Hemiplegia
- ✓ Moderate or severe renal disease
- ✓ Diabetes with end-organ damage
- ✓ Any tumor
- ✓ Leukemia
- ✓ Lymphoma
- ✓ Moderate or severe liver disease
- ✓ Metastatic solid tumor
- ✓ AIDS

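### CRP-based DAS28 is scored with a bare ln(CRP) that has no value at 0 and no floor near 0, and the protocol and SAP print different CRP formulas

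*Protocol*

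**What the plan says.** Protocol 9.2.4.7 gives separate ESR and CRP formulas. The CRP version ends in "0.36 * \ln(\text{CRP}) + 0.014 * (\text{Global assessment of Health in cm}) + 0.96". SAP 3.5.2 gives a single formula for both markers, with the term "0.70 * \ln(\text{ESR or CRP}) + 0.014 * (\text{Global assessment of Health" and no constant. Each document presents its formula as the way DAS28 will be scored.

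The marker is a choice. The protocol step reads "Record the blood test data of erythrocyte sedimentation rate (ESR) or C reactive protein (CRP) using the latest measurement in the medical records". The forms in Appendix C and Appendix K ask for "C-reactive protein (CRP) (in mg/L) of this patient" as the alternative to ESR, with no lower limit and no instruction for a zero or a value below detection. The score itself is optional: "Please record the latest DAS28 score*, if calculated". The footnote reads "For calculation instruction, please refer to study protocol, page 21, clinical case report form (CRF". The table of contents puts the exclusion criteria on page 21 and section 9.2.4.7 on page 25. Protocol 9.2.4.7 also says that "an online scoring calculator for the DAS28 can be found at" a web address, and SAP 3.5.2 refers to such a calculator too.

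SAP 3.5.5 rules out imputation except for a missing day in a date and for PRO items under the developers' rules.

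**The concern.** A scoring rule should return a value for every result that the form accepts. This one does not. CRP of 0 is an admissible entry with no logarithm, and results just above 0 make the term as negative as one likes. Rounding or assay noise at very low CRP could then move a patient across a DAS28 category. The two documents also give different scores for the same patient.

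DAS28 is the entry criterion (above 3.2), separates moderate from severe disease, describes the cohort at baseline, and is the regressor in Tables 10.1 and 10.2. Baseline severity also enters the sensitivity ANOVA for HAQ DI and the modifier models of Table 11. A visit without a score drops out of the regressions, and it would do so because CRP was low.

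**Working it through.** The documents contain no worked DAS28 value, so there is no printed figure to reproduce. The check evaluates the printed terms.

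**Inputs.** Protocol CRP term 0.36·ln(CRP), constant 0.96 (9.2.4.7). SAP term 0.70·ln(CRP), no constant (3.5.2). CRP in mg/L (Appendix C). Low-activity band above 2.6 up to 3.2, width 3.2 − 2.6 = 0.6 (both documents).

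**1. Behaviour near zero, printed formulas only**

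| CRP (mg/L) | 0.36·ln(CRP) | 0.70·ln(CRP) |
|---|---|---|
| 10 | 0.83 | 1.61 |
| 1 | 0 | 0 |
| 0.5 | −0.25 | −0.49 |
| 0.1 | −0.83 | −1.61 |
| 0.01 | −1.66 | −3.22 |
| 0 | undefined | undefined |

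From 1 to 0.1 mg/L the drop is 0.36·ln(10) = 0.83 under the protocol and 0.70·ln(10) = 1.61 under the SAP. Both exceed 0.6.

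**2. Protocol against SAP, same patient.** With the global assessment entered identically, protocol minus SAP = 0.96 + (0.36 − 0.70)·ln(CRP) = 0.96 − 0.34·ln(CRP). This is −0.06 at 20 mg/L, 0.96 at 1 mg/L and 1.74 at 0.1 mg/L. The two agree closely at CRP 20 and are more than a full band apart at CRP 1.

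**3. Against an assumed offset.** The documents contain no offset. If ln(CRP+1) is assumed as comparator with weight 0.36, the bare term is lower by 0.36·ln(1 + 1/CRP). The excess fall from CRP 20 mg/L (gap 0.018) to an assumed follow-up value is:

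- to 5 mg/L: 0.066 − 0.018 = 0.05
- to 3 mg/L: 0.104 − 0.018 = 0.09
- to 1 mg/L: 0.250 − 0.018 = 0.23
- to 0.5 mg/L: 0.396 − 0.018 = 0.38

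**4. Net direction for the whole score.** Take an assumed patient: tender joints 10 to 3, swollen 8 to 2, CRP 20 to 0.5 mg/L, global assessment 6 to 2 cm. The joint terms fall by 0.56·(√10 − √3) + 0.28·(√8 − √2) = 0.80 + 0.40 = 1.20. The CRP term falls by 0.36·ln(40) = 1.33 as printed, or 0.36·ln(21/1.5) = 0.95 with the offset. The global term falls by 0.014·4 = 0.056 in cm, or 0.014·40 = 0.56 if the weight was meant for mm (a second assumption). Total falls:

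- protocol as printed: 2.58
- offset, cm: 2.20
- offset, mm: 2.71
- SAP formula, cm: 3.84

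The printed protocol fall lies between the two offset versions, so its direction of error depends on a unit question that the documents do not settle.

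**The case against.** A reader might infer that DAS28 falls too far once CRP normalises, and hence that improvement is overstated. The documents do not support that. It needs a reference formula, and ln(CRP+1) appears in neither document. A negative log term is not itself an error, because the protocol formula carries a constant. The only low-CRP threshold in the documents is 1 mg/dL, which is 10 mg/L (Protocol 7.0, SAP 1.1). At that level the excess fall from 20 mg/L is 0.034 − 0.018, about 0.02, even under the assumed comparator. It stays under 0.1 at 3 to 5 mg/L. Nothing says how often values near or below 1 mg/L will occur, and step 4 shows that the net direction can go either way.

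Exposure is limited too. ESR may be used instead of CRP, the score may come from the calculator, and entry can be met on either DAS28 version. DAS28 change feeds only exploratory regressions. The footnote names the right section, so its wrong page number is editorial.

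All of this stands, and it removes the directional claim. It does not repair the rule. CRP is permitted on equal terms with ESR, so its formula has to work on every value that the form accepts. Offering a formula and a calculator side by side, with entry optional, means that one variable may mix methods. The disagreement between protocol and SAP needs no outside reference.

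**Conclusion.** The scoring rule fails on admissible data and differs between the documents. That follows from the printed text alone: no value at CRP 0, a drop of 0.83 or 1.61 between 1 and 0.1 mg/L against a 0.6-wide band, and a protocol–SAP gap of 0.96 at 1 mg/L. A CRP-scored visit recorded as 0 is lost from Tables 10.1 and 10.2 only if it has neither an ESR-based nor a calculator score.

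The figures of 0.23 and 0.38 rest on the assumed offset and on assumed CRP values, and the direction of bias in total DAS28 is not established. The primary analysis is an unadjusted paired t-test on HAQ DI change, so it and the sample size are untouched. What is affected is eligibility, severity grouping and the analyses that use DAS28 or baseline severity. The point should be corrected, but it does not threaten the main conclusion.

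**What to change.** - Print one CRP-specific formula, with the same weight and constant, in Protocol 9.2.4.7 and SAP 3.5.2, separate from the ESR formula. State CRP in mg/L and the unit of the global assessment.
- Use a CRP term defined at 0, such as ln(CRP+1), and check it against the calculator to which both documents refer before adopting it. Say how results below detection are entered.
- Derive CRP-based DAS28 centrally with that formula where all components were recorded. The form text as shown has no field for the global assessment, although a field inside a missing figure cannot be excluded. Where a component is absent, record how the score was obtained.
- Correct the page reference on the baseline, follow-up and early-termination forms, preferably by citing the section number.

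The cost is an edit to two passages, a form footnote and the reprogramming of one derived variable. With an offset, CRP-based changes at very low CRP will look smaller than under the printed formulas.
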